11.1.2. Optifoam® Gentle Silicone Border Dressings

Optifoam Gentle silicone border dressings are currently marketed dressings indicated for the management of partial and shallow full-thickness wounds. The dressings aid in providing a moist wound environment and the absorption of exudate, which aids in wound healing. The silicone adhesive is often less traumatic and painful upon removal compared to acrylic based adhesives. The dressings that will be used in this study are available in four sizes: 1/6" x 2", 3" x 3", 4" x 4", and 6" x 6".

Fibrillar dressing for treating chronic, stalled wounds

MED-2018-DIV71-008

23 August 2018

V 1.0

CONFIDENTIAL

11.1.3. CoFlex® TLC Two Layer Compression Bandage System

CoFlex TLC two-layer compression bandage system is a compressive dressing system intended for use to manage venous disease. The first layer of the dressing is a soft foam that wicks away moisture, with the second layer composed of a short stretch cohesive material, providing adaptive compression levels. The device also comes with a nylon stocking to apply over the completed dressing for patient comfort and ease of movement under clothes and on bed sheets. Further information regarding the device can be found below or at <https://www.medline.com/product/CoFlex-TLC-Two-Layer-Compression-System/Multi-Layer-Compression-Systems/Z05-PF11482?question=coflex+tlc&index=P1&indexCount=1>

Fibrillar dressing for treating chronic, stalled wounds

MED-2018-DIV71-008

23 August 2018

V 1.0

CONFIDENTIAL

11.2. Screening Forms

11.2.1. Pre-Screening Form

Pre-Screening Form

MED-2018-DIV71-008: A case series evaluating a fibrillar collagen powder dressing to treat chronic, stalled lower-extremity wounds

Screening #:	Criteria
Age: _____	Between \geq 18
Where is your wound located? _____	Must be below knee
How long has the wound been present? _____	Must be \geq 4 weeks
Have you tried any therapies to heal the wound? If so, what were they? _____	Must have tried at least one type of advanced wound dressing/therapy
Would you be able to visit the clinic twice a week for up to 12 weeks? _____	Must answer yes

This subject is: Continuing in the study Dismissed from the study

If subject is dismissed, please document reason: _____

Form completed by: _____ Date: _____

11.2.2. Screening Form

Screening Form

MED-2018-DIV71-008: A case series evaluating a fibrillar collagen powder dressing to treat chronic, stalled lower-extremity wounds

Subject #: _____	Age: _____
Gender (please check on):  Male  Female	Yes No
Exclusion Criteria	
1. Does the subject have a known sensitivity to collagen?	 
2. Is the subject pregnant, breast feeding, or intending to become pregnant during the duration of the study?	 
3. Does patient have osteomyelitis or an infection in the wound?	 
4. Is the subject unwilling or unable to apply a porcine based product to the wound?	 
Inclusion Criteria	
5. Is the wound located below the knee?	 
6. Is the chronic wound between 1 cm ² to 100 cm ²	 
7. Is the subject's wound duration greater than or equal to four weeks?	 
8. Is the wound a pressure ulcer, diabetic foot ulcer, venous ulcer, ulcer of mixed-vascular origin, post-surgical, or traumatic wound (circle wound type)	 
9. Has the subject tried an advanced wound dressing or therapy to treat the wound without success? If yes, list below: _____	 
10. Biphasic or triphasic Doppler waveform, or Ankle Brachial Index > 0.8 with no worse than mild disease on segmental pressures, taken within last 3 months	 
To qualify for study, subject must:	

• be \geq 18 years old• Have a "No" response for questions 1-4• Have a "Yes" response for questions 5-9	
This subject is: Continuing in the study  Dismissed from the study 	
If subject is dismissed, please document reason: _____	
Form completed by: _____	Date: _____

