1.2. Schedule of Activities (SOA)

REQUIRED ASSESSMENTS	PRE-SCREENING Day -1	SCREENING VISIT Day 0 (May be combined with Initial Visit, Day 1)	INITIAL VISIT Day 1	DRESSING CHANGE VISITS Twice weekly (Every 3 days ± 1 day)	WOUND ASSESSMENT VISITS Once per week Every 7 days ± 2 days (May be combined with Dressing Change Visit)	FINAL VISIT 12 weeks from Initial Visit ³
Pre-Screening Questionnaire ¹	X					
Informed Consent		X				
Screening Form to assess eligibility		X				
Decision on eligibility		X				
Demographics			X			
Wound History			X			
Wound Photograph			X		X	X
Bates-Jensen Wound Assessment			X		X	X
Application of Puracol® Ultra			X	X	X ²	
Pain Assessment for dressing change			X		X	X
Secondary Dressing Notation			X	X	X ²	
Adverse Event Assessment		X	X	X	X	X

1: For participants contacting the research facility, 2: If combined with Dressing change visit, 3: Final visit may occur earlier in the event the participant's wound has completely healed before 12 weeks

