5. STUDY POPULATION

5.1. Inclusion Criteria

In order to participate in the study, a participant must meet *ALL* of the following criteria:

- Age 18+
- Has one of the following types of wounds below the knee:
 - Diabetic ulcers
 - Pressure ulcers
 - Venous ulcers
 - Ulcers of mixed-vascular origin
 - Traumatic wounds
 - Post-surgical wounds
- Wound has been present for at least four weeks
- Wound is free of necrotic tissue or debridement practices will take place prior to initial visit in order to remove necrotic tissue.
- Wound has not responded to at least one type of advanced wound care treatment
- Wound size is between 1 and 100 cm²
- Patient has adequate circulation as demonstrated by biphasic or triphasic Doppler waveform, measured within three months prior to study enrollment. If monophasic on exam, then non-invasive tests must display Ankle Brachial Index greater than 0.8 and no worse than mild disease on segmental pressures.
- Wound is confirmed as being free of infection and absence of osteomyelitis.

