6.2.2. Screening

After obtaining informed consent, research staff will assess eligibility to participate in the study using the screening form provided in Appendix 11.2.2. Participants who qualify will be assigned a subject number. In the event the potential subject has not had a measurement to determine adequate blood flow in the past three months, the PI or research staff will assess blood flow via a handheld vascular Doppler device. Subjects must meet the Doppler criteria mentioned in section 5.1 of this protocol to be randomized

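### The screening form's qualifying rule stops at question 9 and leaves out the circulation criterion (question 10) that Sections 5.1 and 6.2.2 make mandatory

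*Combined protocol and SAP*

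**What the plan says.** Section 5.1 opens with "In order to participate in the study, a participant must meet *ALL* of the following criteria". One of the criteria is "Patient has adequate circulation as demonstrated by biphasic or triphasic Doppler waveform, measured within three months prior to study enrollment", with an alternative route through the Ankle Brachial Index and segmental pressures when the waveform is monophasic.

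Section 6.2.2 says that "research staff will assess eligibility to participate in the study using the screening form provided in Appendix 11.2.2". The same paragraph provides for a handheld Doppler check where no measurement from the past three months exists, and makes the Section 5.1 Doppler criteria a condition of going forward.

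The Schedule of Activities (Section 1.2) puts "Screening Form to assess eligibility" and "Decision on eligibility" at the same Screening Visit.

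The form in Appendix 11.2.2 has questions 1-4 under its exclusion heading and 5-10 under its inclusion heading. Question 10 reads "Biphasic or triphasic Doppler waveform, or Ankle Brachial Index > 0.8 with no worse than mild disease on segmental pressures", with a three-month window and its own Yes and No boxes. Below the questions, under "To qualify for study, subject must", there are three conditions: age at least 18, No to questions 1-4, and Yes as the "response for questions 5-9". The tick-boxes for continuing or dismissing the subject follow directly.

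**The concern.** The form asks the circulation question and labels it an inclusion criterion, then omits it from the rule that turns answers into a decision. Question 10 is the only one of the ten numbered questions that the rule does not use. The form does not say that a No to question 10 is acceptable; it simply does not list it.

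What is at stake is the match between the enrolled patients and the population defined in Section 5.1. Staff who follow the printed rule could mark a subject as continuing although Sections 5.1 and 6.2.2 exclude that subject. Nothing in the analysis plan would remove such a participant afterwards: the evaluable dataset in Section 8.2 depends on valid initial and final wound assessments and on compliance with at least 75% of dressing changes, not on eligibility.

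**Working it through.** The plan gives no figure to reproduce here. The check sets the form against the protocol body.

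**Inputs**

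- Inclusion questions on the form (Appendix 11.2.2): 5, 6, 7, 8, 9, 10.
- Questions for which the rule requires Yes (same form): 5, 6, 7, 8, 9.
- Questions for which the rule requires No (same form): 1, 2, 3, 4.
- Status of circulation in the protocol body: mandatory (Sections 5.1 and 6.2.2).

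**Step 1: coverage of the rule.** There are 6 inclusion questions and 5 required Yes answers, so 6 − 5 = 1 is left out. That one is question 10, circulation.

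**Step 2: answer patterns that satisfy the rule.** For an adult, questions 1-9 are each fixed at one answer (1 way) and question 10 is free (2 ways): 1 × 2 = 2 patterns. If the rule ran to question 10, there would be 1 × 1 = 1 pattern. The extra pattern is the one in conflict:

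| Adult subject | Form's rule, read as the complete list | Sections 5.1 and 6.2.2 |
|---|---|---|
| No to 1-4, Yes to 5-9, Yes to 10 | qualifies | circulation criterion met |
| No to 1-4, Yes to 5-9, No to 10 | qualifies | excluded |

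**Step 3: is the criterion recorded or enforced on another form?** The pre-screening form (11.2.1) has no circulation item. The Initial Visit case report form (11.3.1) has no Doppler or Ankle Brachial Index field. Of the study forms shown, the screening form is the only one that records this criterion. No section makes circulation optional or adds question 10 to the form's rule.

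**Step 4: weight of one such participant.** With 20 planned participants (Sections 4.1 and 8.1), one is 1/20 = 5% of enrolment. This gives the scale of a single error; it does not say how likely one is.

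**The case against.** The strongest reply is that the form lists things a subject must satisfy, which are necessary conditions, and never says that they suffice. The form is also plainly not a full copy of the protocol: it has no question on necrotic tissue or debridement (Section 5.1) and none on the investigator's judgement of ability to comply (Section 5.2). Staff must therefore apply Sections 5.1 and 5.2 in any case. On that reading the line is incomplete but permits nothing that the protocol forbids.

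There are safeguards too. Section 6.2.2 states the Doppler requirement in the very paragraph that names the form. A No to question 10 would stand in plain view under the inclusion heading. Monitoring under Section 9.2 covers subject eligibility, and Section 9.4 requires deviations to be identified and reported.

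Most of this stands, and it is why the point is minor. It does not remove the discrepancy. Section 6.2.2 makes this form the eligibility tool, and the rule sits just above the decision boxes, so reading it as the complete list is natural. Question 10 also differs from the criteria the form never asks about: here the form asks, classes the item as inclusion, and then leaves it out of its own rule. Monitoring is required at least every two months, so detection may come after enrolment.

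One cited sentence has a flaw of its own: Section 6.2.2 ties the Doppler requirement to randomization, although this single-group case series has none. The intent is clear, and Section 5.1 carries the requirement alone.

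**Conclusion.** The concern holds and is minor. The form's qualifying rule omits one of its six inclusion questions, and that question is a mandatory criterion in Sections 5.1 and 6.2.2. The conflict in outcome rests on reading the rule as the complete list of conditions. On the narrower reading, the line is still incomplete against the form's own inclusion heading.

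It is probably a numbering slip. The protocol body governs and the practical risk is small. The documents give no basis for estimating how often a subject with a No to question 10 would be enrolled. The sample of 20 was chosen without a power analysis, and no planned statistical figure is affected.

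**What to change.** Correct the qualifying line in Appendix 11.2.2 so that the required Yes responses run over questions 5-10, in agreement with Sections 5.1 and 6.2.2. The cost is one corrected line on one form. No criterion, procedure or data field is added, because the protocol body already requires the circulation measurement and question 10 already records it. The change does not make the form a full restatement of Sections 5.1 and 5.2; it only makes the form's rule use every question the form asks.

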11.3. Case Report Forms

11.3.1. Initial Visit Case Report Form

Initial Visit Case Report Form		
MED-2018-DIV71-008: A case series evaluating a fibrillar collagen powder dressing to treat chronic, stalled lower-extremity wounds		
Demographic Data		
Subject Number:	Age:	Gender: Male  Female 
Height (in):	Weight (lbs):	
Race (may select more than one): Black  White  Asian  Hispanic  Other 		
Relevant Medical Diagnoses and Current Medications:		
Wound History		
Wound Type:		
Wound Location:		
Duration of wound (in months):		
Prior treatments and duration:		
Has mechanical debridement been performed?		Yes  No 
Form Completed by:		Date:

11.3.2. Wound Photo Case Report Form

Wound Photo Case Report Form

MED-2018-DIV71-008: A case series evaluating a fibrillar collagen powder dressing to treat chronic, stalled lower-extremity wounds

Place photograph of the wound below:

Subject Number: _____ **Date:** _____ **Wound Assessment Number:** _____

Wound Size: _____ cm² (enter value obtained from camera software platform)

Current Pain Rating: _____ **Dressing Change Pain Rating:** _____

11.3.3. Bates-Jensen Wound Assessment Tool (BWAT)

11.3.3.1. BWAT Instructions for use

General Guidelines:

Fill out the attached rating sheet to assess a wound's status after reading the definitions and methods of assessment described below. Evaluate once a week and whenever a change occurs in the wound. Rate according to each item by picking the response that best describes the wound and entering that score in the item score column for the appropriate date. When you have rated the wound on all items, determine the total score by adding together the 13-item scores. The HIGHER the total score, the more severe the wound status. Plot total score on the Wound Status Continuum to determine progress. If the wound has healed/resolved, score items 1,2,3 and 4 as =0.

Specific Instructions:

1. **Size:** Use ruler to measure the longest and widest aspect of the wound surface in centimeters; multiply length x width. Score as = 0 if wound healed/resolved.
2. **Depth:** Pick the depth, thickness, most appropriate to the wound using these additional descriptions, score as
0 = if wound healed/resolved:
1 = tissues damaged but no break in skin surface.
2 = superficial, abrasion, blister or shallow crater. Even with, &/or elevated above skin surface (e.g., hyperplasia).
3 = deep crater with or without undermining of adjacent tissue. 4 = visualization of tissue layers not possible due to necrosis. 5 = supporting structures include tendon, joint capsule.
3. **Edges:** Score as = 0 if wound healed/resolved. Use this guide:

Indistinct, diffuse	=	unable to clearly distinguish wound outline.
Attached	=	even or flush with wound base, no sides or walls present; flat.
Not attached	=	sides or walls are present; floor or base of wound is deeper than edge.
Rolled under, thickened	=	soft to firm and flexible to touch.
Hyperkeratosis	=	callous-like tissue formation around wound & at edges.
Fibrotic, scarred	=	hard, rigid to touch.
4. **Undermining:** Score as = 0 if wound healed/resolved. Assess by inserting a cotton tipped applicator under the wound edge; advance it as far as it will go without using undue force; raise the tip of the applicator so it may be seen or felt on the surface of the skin; mark the surface with a pen; measure the distance from the mark on the skin to the edge of the wound. Continue process around the wound. Then use a transparent metric measuring guide with concentric circles divided into 4 (25%) pie-shaped quadrants to help determine percent of wound involved.
5. **Necrotic Tissue Type:** Pick the type of necrotic tissue that is predominant in the wound according to color, consistency and adherence using this guide:

White/gray non-viable tissue	=	may appear prior to wound opening; skin surface is white or gray.
Non-adherent, yellow slough	=	thin, mucinous substance; scattered throughout wound bed; easily separated from wound tissue.
Loosely adherent, yellow slough	=	thick, stringy, clumps of debris; attached to wound tissue.
Adherent, soft, black eschar	=	soggy tissue; strongly attached to tissue in center or base of wound.
Firmly adherent, hard/black eschar	=	firm, crusty tissue; strongly attached to wound base and edges (like a hard scab).

© 2001 Barbara Bates-Jensen Used with permission

6. **Necrotic Tissue Amount:** Use a transparent metric measuring guide with concentric circles divided into 4 (25%) pie-shaped quadrants to help determine percent of wound involved.
7. **Exudate Type:** Some dressings interact with wound drainage to produce a gel or trap liquid. Before assessing exudate type, gently cleanse wound with normal saline or water. Pick the exudate type that is predominant in the wound according to color and consistency, using this guide:

Bloody	=	thin, bright red
Serosanguineous	=	thin, watery pale red to pink
Serous	=	thin, watery, clear
Purulent	=	thin or thick, opaque tan to yellow or green may have offensive odor

8. **Exudate Amount:** Use a transparent metric measuring guide with concentric circles divided into 4 (25%) pie- shaped quadrants to determine percent of dressing involved with exudate. Use this guide:

None	=	wound tissues dry.
Scant	=	wound tissues moist; no measurable exudate.
Small	=	wound tissues wet; moisture evenly distributed in wound; drainage involves $\leq 25\%$ dressing.
Moderate	=	wound tissues saturated; drainage may or may not be evenly distributed in wound; drainage involves $> 25\%$ to $\leq 75\%$ dressing.
Large	=	wound tissues bathed in fluid; drainage freely expressed; may or may not be evenly distributed in wound; drainage involves $> 75\%$ of dressing.

9. **Skin Color Surrounding Wound:** Assess tissues within 4cm of wound edge. Dark-skinned persons show the colors "bright red" and "dark red" as a deepening of normal ethnic skin color or a purple hue. As healing occurs in dark-skinned persons, the new skin is pink and may never darken.
10. **Peripheral Tissue Edema & Induration:** Assess tissues within 4cm of wound edge. Non-pitting edema appears as skin that is shiny and taut. Identify pitting edema by firmly pressing a finger down into the tissues and waiting for 5 seconds, on release of pressure, tissues fail to resume previous position and an indentation appears. Induration is abnormal firmness of tissues with margins. Assess by gently pinching the tissues. Induration results in an inability to pinch the tissues. Use a transparent metric measuring guide to determine how far edema or induration extends beyond wound.
11. **Granulation Tissue:** Granulation tissue is the growth of small blood vessels and connective tissue to fill in full thickness wounds. Tissue is healthy when bright, beefy red, shiny and granular with a velvety appearance. Poor vascular supply appears as pale pink or blanched to dull, dusky red color.
12. **Epithelialization:** Epithelialization is the process of epidermal resurfacing and appears as pink or red skin. In partial thickness wounds it can occur throughout the wound bed as well as from the wound edges. In full thickness wounds it occurs from the edges only. Use a transparent metric measuring guide with concentric circles divided into 4 (25%) pie-shaped quadrants to help determine percent of wound involved and to measure the distance the epithelial tissue extends into the wound.

©2001 Barbara Bates-Jensen Used with permission

11.3.3.2. BWAT Case Report Form

Subject Number: _____ Date: _____ Assessment Number: _____

Complete the rating sheet to assess wound status. Evaluate each item by picking the response that best describes the wound and entering the score in the item score column for the appropriate date. If the wound has healed/resolved, score items 1,2,3, & 4 as =0.

Location: Anatomic site. Circle, identify right (R) or left (L) and use "X" to mark site on body diagrams:

Sacrum & coccyx

Lateral ankle

Trochanter

Medial ankle

Ischial tuberosity

Heel

Buttock

Other site:

Shape: Overall wound pattern; assess by observing perimeter and depth.

Circle and date appropriate description:

Irregular

Linear or elongated

[figure not shown]
Round/oval

Bowl/boat

Square/rectangle

Butterfly

Other Shape

Item	Assessment	Date Score
1. Size*	*0 = Healed, resolved wound 1 = Length x width <4 sq cm 2 = Length x width 4-≤16 sq cm 3 = Length x width 16.1-≤36 sq cm 4 = Length x width 36.1-≤80 sq cm 5 = Length x width >80 sq cm	
2. Depth*	*0 = Healed, resolved wound 1 = Non-blanchable erythema on intact skin 2 = Partial thickness skin loss involving epidermis &/or dermis 3 = Full thickness skin loss involving damage or necrosis of subcutaneous tissue; may extend down to but not through underlying fascia; &/or mixed partial & full thickness &/or tissue layers obscured by granulation tissue 4 = Obscured by necrosis 5 = Full thickness skin loss with extensive destruction, tissue necrosis or damage to muscle, bone or supporting structures	
3. Edges*	*0 = Healed, resolved wound 1 = Indistinct, diffuse, none clearly visible 2 = Distinct, outline clearly visible, attached, even with wound base 3 = Well-defined, not attached to wound base 4 = Well-defined, not attached to base, rolled under, thickened 5 = Well-defined, fibrotic, scarred or hyperkeratotic	
4. Under-mining*	*0 = Healed, resolved wound 1 = None present 2 = Undermining < 2 cm in any area 3 = Undermining 2-4 cm involving < 50% wound margins 4 = Undermining 2-4 cm involving > 50% wound margins 5 = Undermining > 4 cm or Tunneling in any area	
5. Necrotic Tissue Type	1 = None visible 2 = White/grey non-viable tissue &/or non-adherent yellow slough 3 = Loosely adherent yellow slough 4 = Adherent, soft, black eschar 5 = Firmly adherent, hard, black eschar	

Fibrillar dressing for treating chronic, stalled wounds

MED-2018-DIV71-008

[figure not shown]
23 August 2018

V 1.0

CONFIDENTIAL

6. Necrotic Tissue Amount	1 = None visible 2 = < 25% of wound bed covered 3 = 25% to 50% of wound covered 4 = > 50% and < 75% of wound covered 5 = 75% to 100% of wound covered	
7. Exudate Type	1 = None 2 = Bloody 3 = Serosanguineous: thin, watery, pale red/pink 4 = Serous: thick, watery, clear 5 = Purulent: thin or thick, opaque, tan/yellow, with or without odor	
8. Exudate Amount	1 = None, dry wound 2 = Scant, wound moist but no observable exudate 3 = Small 4 = Moderate 5 = Large	
9. Skin Color Surrounding Wound	1 = Pink or normal for ethnic group 2 = Bright red &/or blanches to touch 3 = White or grey pallor or hypopigmented 4 = Dark red or purple &/or non-blanchable 5 = Black or hyperpigmented	
10. Peripheral Tissue Edema	1 = No swelling or edema 2 = Non-pitting edema extends < 4cm around wound 3 = Non-pitting edema extends \geq 4cm around wound 4 = Pitting edema extends < 4cm around wound 5 = Pitting edema extends \geq 4cm around wound	
11. Peripheral Tissue Induration	1 = None present 2 = Induration < 2cm around wound 3 = Induration 2-4cm extending <50% around wound 4 = Induration 2-4cm extending \geq 50% around wound 5 = Induration > 4cm in any area around wound	
12. Granulation Tissue	1 = Skin intact or partial thickness wound 2 = Bright, beefy red; 75% to 100% of wound filled &/or tissue overgrowth 3 = Bright, beefy red; <75% & >25% of wound filled 4 = Pink, &/or dull, dusky red &/or fills \leq 25% of wound 5 = No granulation tissue present	
13. Epithelialization	1 = 100% wound covered, surface intact 2 = 75% to < 100% wound covered &/or epithelial tissue extends > 0.5cm into wound bed 3 = 50% to < 75% wound covered &/or epithelial tissue extends < 0.5cm into wound bed 4 = 25% to < 50% wound covered 5 = < 25% wound covered	
Total Score		
Signature		

Plot the total score on the Wound Status Continuum by putting an "X" on the line and the date beneath the line.

© 2001 Barbara Bates-Jensen Used with permission

Fibrillar dressing for treating chronic, stalled wounds

MED-2018-DIV71-008

23 August 2018

V 1.0

CONFIDENTIAL

